### 13.3. Clinical Laboratory Sampling

Non-fasting blood samples for clinical laboratory analysis will be collected by a qualified staff member at Visit 1 and Visit 13. Approximately 7.5 mL of blood will be collected for each chemistry sample and 3 ml of blood will be collected for each complete blood count (CBC). These blood samples will be sent to a central laboratory for analysis. Refer to the study specific laboratory manual for instructions regarding handling of the blood samples and shipping instructions.

The following tests, at a minimum, will be conducted:

Chemistry Panel	Complete Blood Count
Albumin	Hematocrit

Aclaris Therapeutics, Inc.

Protocol Number: A-101-WART-301

Amendment 3: Version 5 14 February 2019

Alkaline phosphatase	Hemoglobin
Alanine aminotransferase (ALT)	Platelet count
Aspartate aminotransferase (AST)	Red blood cell morphology
Blood urea nitrogen (BUN)	Red blood cell count
Bicarbonate	White blood cell count
Calcium	White blood cell differential
Chloride	% & absolute
Creatinine	Basophils
Glucose	Eosinophils
Lactate dehydrogenase (LDH)	Lymphocytes
Phosphorus	Monocytes
Potassium	Neutrophils
Sodium	
Total bilirubin	
Total protein	
Uric acid	

The results of the clinical laboratory tests will be reported on the central laboratory's standard reports. These laboratory results will be sent to the investigator via fax. The investigator must review all laboratory reports in a timely manner and note NCS or CS to define the clinical relevance of any result that is outside the normal range for the laboratory. The investigator must date and initial every laboratory report.

The investigator must review the Visit 1 laboratory results for all the measured analytes for each subject prior to Visit 2. The subject must not be randomized at Visit 2 if any of the Visit 1 results are outside normal range for the laboratory AND, in the opinion of the investigator, CS.

The investigator must report all laboratory results that are BOTH outside the normal range for the laboratory AND, in the opinion of the investigator, CS as medical history if found prior to the first study medication treatment or as an AE if found after the first study medication treatment begins.

#### **13.4. Demographics and Medical History**

At Visit 1, the investigator or designee will collect demographic information including date of birth, sex at birth, race and, if appropriate, ethnicity for each subject.

At Visit 1, the investigator must determine each subject's Fitzpatrick skin type and document appropriately on the subject's CRF.

**Table 4: Fitzpatrick Skin Type Scoring System**

Skin Type Classification	Description
Type I	always burns, never tans (pale white; blond or red hair; blue eyes; freckles)
Type II	usually burns, tans minimally (white; fair; blond or red hair; blue, green, or hazel eyes)
Type III	sometimes mild burn, tans uniformly (cream white; fair with any hair or eye color)
Type IV	burns minimally, always tans well (moderate brown)
Type V	very rarely burns, tans very easily (dark brown)
Type VI	Never burns, never tans (deeply pigmented dark brown to darkest brown)

(Fitzpatrick, TB, 1988)

Medical history information will be recorded including all medical conditions and disease states that, at Visit 1:

- Are ongoing
- Require concomitant therapy

Are, in the opinion of the investigator, relevant to the subject's study participation.

## 14. ADVERSE EVENTS

### 14.1. Definitions

#### 14.1.1. Adverse Events (AEs)

An adverse event (AE) is any untoward medical occurrence in a patient that develops or worsens in severity during the conduct of a clinical study of a pharmaceutical product and does not necessarily have a causal relationship to the study drug. An adverse event can, therefore, be any unfavorable and unintended physical sign, symptom, or laboratory parameter that develops or worsens in severity during the course of the study, or significant worsening of the disease under study (or any concurrent disease), whether or not considered related to the study drug.

Accordingly, an adverse event could include any of the following:

- intercurrent illnesses;
- physical injuries;
- events possibly related to concomitant medication;
- significant worsening (change in nature, severity, or frequency) of the disease under study or other pre-existing conditions. (NOTE: A condition, recorded as pre-existing, that is intermittently symptomatic [e.g., headache] and which occurs during the study should be recorded as an adverse event);
- Drug interactions;
- Events occurring during diagnostic procedures or any washout phase of the study;
- laboratory or diagnostic test abnormalities occurring after the start of the study (i.e., after screening and once confirmed by repeat testing) that results in the withdrawal of the patient from the study, requires medical treatment or further diagnostic work-up, or is considered by the study investigator to be clinically significant. NOTE: Abnormal laboratory test results at the screening visit that preclude a patient from entering the study or receiving study treatment are not considered adverse events, but will be recorded to monitor data from patients who do not meet screening criteria.

**Worsening of any of the identified common wart assessments should be reported as an AE ONLY if the use of the study medication is interrupted or discontinued or if therapy is required to manage the event.**

**The investigator must, for any common wart related AE, question the subject in detail to determine if there are any confounding factors (e.g., irritation by clothing or activity, sunburn) for any such AE.**

The investigator should, when certain, report a diagnosis rather than the signs, symptoms or clinically relevant abnormal laboratory values associated with the AE. Otherwise, signs, symptoms or abnormal laboratory values may be used to describe the AE.

Any CS abnormality discovered prior to the first study medication treatment should be reported as medical history, not as an AE.

#### **14.1.2. Serious Adverse Events (SAEs)**

A Serious Adverse Event is any untoward medical occurrence that at any dose:

- Results in death;
- Is life threatening;
- Requires inpatient hospitalization or prolongation of existing hospitalization;
- Results in persistent or significant disability/incapacity,
- Is a congenital anomaly/birth defect or
- Is an important medical event.

The term “life threatening” refers to an event in which the subject was at risk of death at the time of event; it does not refer to an event that hypothetically might have caused death if it was more severe.

Inpatient hospitalization is considered to have occurred if the subject is admitted to the hospital on an inpatient basis, even if released the same day. Prolongation of hospitalization is defined as an additional night stay in the hospital. Hospitalization for elective treatment of a pre-existing condition that did not worsen from baseline is not considered an AE.

Important medical events are those that may not be immediately life threatening, result in death or hospitalization, but are clearly of major clinical significance and may jeopardize the subject or require intervention to prevent one of the outcomes listed in the SAE definition above. These should also usually be considered serious. Examples of such events are intensive treatment in an emergency room or at home for allergic bronchospasm, blood dyscrasia or convulsions that do not result in hospitalization.

#### **14.1.3. Adverse Event Reporting Period**

The investigator must start reporting non-serious AEs starting with the subject’s first study medication treatment continuing until Visit 11. Non-serious adverse events that occur between the time the subject was consented and the first application of study medication will be reported as medical history.

Reporting for SAEs begins after the subject signs the informed consent and continues until Visit 11 (regardless of relationship to study medication). If a subject experiences a SAE after Visit 11 that is deemed by the investigator to be related to study medication, the investigator must report this to the Sponsor using the study specific SAE report form.

#### **14.1.4. Severity**

The investigator must define the severity of each AE using the following definitions as a guideline. The investigator will consider the range of the possible severity of the event and identify the severity that is the most appropriate according to her/his medical judgment.

**Mild** – Awareness of signs or symptom, but easily tolerated

**Moderate** – Discomfort, enough to cause interference with usual activity

**Severe** – Incapacitating with inability to perform usual activity.

#### **14.1.5. Relationship to Study Medication**

The investigator will determine if there is a reasonable causal relationship between the study medication and an AE or not. The investigator will use her/his best medical judgment and consider all relevant factors (*e.g.*, temporal relationship, location of the event, the subject's relevant medical history, concomitant therapies and concurrent conditions) to determine the relationship of the AE to the study medication. The investigator will define the relationship of an AE to the study medication by selecting one of the following categories.

**Related** – There is a reasonable possibility that there is a causal relationship between the study medication and the AE.

**Not Related** – There is not a reasonable possibility that there is a causal relationship between the study medication and the AE.

The term “reasonable causal relationship” means there are facts or arguments to suggest a causal relationship (International Conference on Harmonization (ICH) E2A).

### **14.2. Reporting Procedures**

#### **14.2.1. Procedures for Reporting Adverse Events**

At each post enrollment visit, the investigator or designee will question the subject to elicit AEs using a non-directive question such as “Has there been any change in your health since the previous study visit?”

The Investigator/designee will monitor the subject for at least 20 minutes after the Treatment Completion Time at any visit during which a study medication treatment is performed to elicit AEs in a similar manner.

If appropriate, based on the subject's response to non-directed questioning regarding AEs, the investigator or designee will follow-up with directed questions and appropriate evaluations.

Any AE noted during the reporting period must be reported in the source documents and on the appropriate AE CRF.

AEs that are defined as “Not Related” to the study medications will be followed until they are resolved or until the subject's last study visit. AEs that are defined as “Related” to the study medications will be followed until they are resolved or, if not resolved after the subject's last study visit, until in the opinion of the investigator, the AE reaches a clinically stable outcome with or without sequelae.

#### **14.2.2. Procedure for Reporting Serious Adverse Events**

Upon becoming aware of a SAE occurring during the AE reporting period, whether or not related to the study medications, the investigator must:

1. Take the appropriate medical action to ensure the subject's safety

Aclaris Therapeutics, Inc.

Protocol Number: A-101-WART-301

Amendment 3: Version 5 14 February 2019

2. Immediately inform Aclaris of the SAE:

**Serious Adverse Event [contact]**

3. Within 24-hours of becoming aware of the event, a SAE report form, an AE CRF and any other relevant information (*e.g.*, concomitant medication CRF, medical history CRF, laboratory test results) must be faxed to the SAE Fax line listed above.
4. Monitor and document the progress of the SAE until it resolves or, if not resolved after the subject's last study visit, until in the opinion of the investigator the AE reaches a clinically stable outcome with or without sequelae AND the investigator and Drug Safety Monitor agree that the SAE is satisfactorily resolved.
5. Inform the Drug Safety Monitor of SAE updates by telephone followed by an SAE form update sent by fax or by e-mail.

Comply with the appropriate regulatory requirements and Aclaris Therapeutics, Inc. instructions regarding reporting of the SAE to the responsible Institutional Review Board (IRB) or Ethics Committee (EC).

#### **14.2.3. Withdrawal Due to an Adverse Event**

Any patient who experiences an adverse event may be withdrawn from study drug at any time at the discretion of the investigator. If a patient is withdrawn wholly or in part because of an adverse event, both the adverse events page and termination page of the CRF will be completed at that time. The patient will be monitored until the event has resolved or stabilized, until a determination of a cause unrelated to the study drug or study procedure is made, or until the patient is referred to the care of a local health care professional. The investigator must inform the medical monitor as soon as possible of all patients who are being considered for withdrawal due to adverse events. Additional reports must be provided when requested.

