### **8.3. Removal of Subjects from Study Therapy**

A subject may be removed from the study therapy for a variety of reasons, including:

- Unacceptable adverse event
- Subject unwilling or refusal to continue with the protocol defined study visits and/or consent withdrawal for study participation
- Change in compliance with an inclusion/exclusion criteria
- Use of a prohibited medication (through Visit 13)
- General or specific changes in the subject's condition that render the subject unacceptable for further treatment in this study in the judgement of the investigator.

Aclaris Therapeutics, Inc.

Protocol Number: A-101-WART-301

Amendment 3: Version 5 14 February 2019

If a subject is to be withdrawn from the study, the Aclaris Therapeutics, Inc. CRA or designee must be informed within 24 hours of the decision to remove the subject from the study.

The study may be discontinued at the discretion of Aclaris Therapeutics, Inc. Some examples of reasons for discontinuation are the occurrence of the following:

- Increased frequency, severity or duration of known AEs
- Medical, regulatory or ethical reasons affecting the continued performance of the study
- Difficulties in the recruitment of subjects

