#### **8.4. Withdrawal Procedures**

If a subject withdraws from the study prior to Visit 13, the reason for and the date of withdrawal from the study must be recorded on the eCRF. If the reason for withdrawal is an adverse event or a clinically significant abnormal laboratory test result, monitoring of the subject will continue until the event has resolved or stabilized, until the patient is referred to the care of a local health care professional, or until a determination of a cause unrelated to the study drug or study procedure is made.

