### **15.3. Statistical Analysis of Efficacy**

The ITT population will be used for primary and secondary efficacy analyses and summaries. The ITT population is defined as all subjects randomized to the study and analyzed as randomized. The Per-Protocol (PP) population will be used for sensitivity analyses for the primary efficacy analysis and all secondary efficacy analyses included in the hierarchical testing procedure. Details on all analyses discussed below will be provided in the study Statistical Analysis Plan (SAP).

The primary efficacy analysis will be a treatment comparison of A-101 45% compared to Vehicle at Visit 10 (Day 60). It will be based on the proportion of subjects who achieve complete clearance (PWA=0) of all identified common warts. A Cochran Mantel Haenszel

(CMH) test stratified by the baseline number of treated warts will be used to perform the primary efficacy comparison between treatment groups, with 2-tail alpha set at 0.05. The analysis will be based on the ITT population. Any identified common wart for a randomized subject that has missing data at the endpoint visit will be treated as not Clear for the purpose of the primary efficacy analysis.

The first sensitivity analysis for the primary endpoint will be an analysis based upon the PP population. This analysis will use the same CMH model described for the primary analysis. A second sensitivity analysis will be conducted for the primary endpoint using the same CMH model for the ITT population that includes the imputation of missing PWA data using a fully conditionally specified (FCS) regression-based Multiple Imputation (MI) procedure. To assess the impact of missing data imputation on the primary analysis results a tipping point analysis will be conducted. This analysis will shift the treatment coefficient in the regression model used in the MI procedure to impose a worse mean maximum PWA for the A-101 45% arm and a better mean maximum PWA for the vehicle arm. Details of this tipping point analysis will be specified in the SAP. In addition, a model similar to the primary analysis model but stratified instead by Study Center will be performed as a sensitivity analysis including a Breslow-Day test to evaluate heterogeneity across sites.

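### Sections 14.2.3, 8.3 and 8.4 do not separate stopping study drug from leaving the study, so subjects permanently off drug can lose their scheduled efficacy and safety assessments

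*Protocol*

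**What the plan says.** Section 14.2.3 opens with study drug: "Any patient who experiences an adverse event may be withdrawn from study drug at any time at the discretion of the investigator". The next sentence, on a subject withdrawn wholly or partly for an adverse event, says "both the adverse events page and termination page of the CRF will be completed at that time". What then continues is follow-up of the event: "The patient will be monitored until the event has resolved or stabilized", or until an unrelated cause is found or local care takes over.

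Section 8.3 is headed and introduced as removal from therapy: "A subject may be removed from the study therapy for a variety of reasons". One listed reason is "Use of a prohibited medication (through Visit 13" (closing bracket omitted here). The text after the list no longer speaks of therapy but of withdrawing the subject from the study.

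Section 8.4 covers withdrawal from the study before Visit 13. It says "the reason for and the date of withdrawal from the study must be recorded on the eCRF" and, for an adverse event or a clinically significant laboratory result, gives nearly the same monitoring rule as 14.2.3. It asks for no final PWA, LSR grading, vital signs or laboratory sample.

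Section 15.3 analyses all randomized subjects. For the primary endpoint, a wart with "missing data at the endpoint visit will be treated as not Clear"; the first secondary analysis applies the same rule at Day 137.

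**The concern.** Stopping medication and ending participation are different events, and an intention-to-treat analysis needs outcomes after the first. If a site reads 14.2.3 and 8.3 as one status, an eligible subject who permanently stops drug has the termination page filled in and is not seen again on schedule. (Ineligible subjects, handled in Section 16.2, are a separate matter.)

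Three things are then at stake.

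- **Efficacy.** The subject's warts may be clear at Day 60 or Day 137, but the subject counts as a non-responder without having been observed.
- **Missing-data sensitivity analyses.** Multiple imputation can use the PWAs recorded before the subject left, but has few or no post-stop outcomes from comparable subjects. The tipping-point analysis tests the assumption and recovers no data.
- **Safety.** Visit 13 laboratory results and vital signs, and late LSR grades, would tend to describe subjects who tolerated treatment.

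This is a question of which data are collected, so a statistical analysis plan cannot repair it afterwards.

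**Working it through.** **1. The passages side by side**

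- 14.2.3: the trigger is withdrawal from drug; the form completed is the termination page.
- 8.4: the trigger is withdrawal from the study; the follow-up of the event is almost identical to 14.2.3. The two statuses therefore get the same procedure.
- 8.3: the trigger is removal from therapy; the consequence described is removal from the study.
- Timing: the last application is Day 53 (Sections 7 and 10.5) and Visit 13 is Day 137. 137 − 53 = 84 days during which no study therapy remains to be removed. Of these, 137 − 60 = 77 days fall after the primary assessment at Visit 10.
- Schedule (Table 2, Sections 13.2 and 13.3): laboratory samples at Visits 1 and 13 only; vital signs at Visits 1, 9 and 13. A subject who leaves before Visit 13 has no post-baseline laboratory sample.

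**2. The plan's own power figure**

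Section 15.1 gives 250 per arm, a difference of at least 11 points in subject responder rates, power above 90%, and 97% by simulation; Section 15.3 sets two-sided alpha at 0.05. Subject-level rates by arm are not given, so the vehicle rate pV is an assumption, with pA = pV + 0.11. With p̄ the mean of the two rates:

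power = Φ{ [(pA − pV)√n − 1.96√(2p̄(1 − p̄))] / √[pA(1 − pA) + pV(1 − pV)] }

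| pV | pA | Power, n = 250 per arm |
|---|---|---|
| 2% | 13% | 99.7% |
| 5% | 16% | 98.1% |
| 7% | 18% | 96.3% |
| 9% | 20% | 94.0% |
| 12% | 23% | 90.2% |

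The claim of more than 90% holds over the whole range. The simulated 97% fits a vehicle rate near 6-7%, so 18% against 7% is used below.

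**3. Points lost when stoppers are scored not Clear**

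Loss in an arm = stop rate × responder rate, assuming stoppers would have cleared at that arm's full rate. The stop rates (3-8% active, 1% vehicle) are assumptions; the protocol gives none.

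- Active: 0.03 × 18% = 0.54 points; 0.08 × 18% = 1.44 points.
- Vehicle: 0.01 × 7% = 0.07 points.
- Net: 0.54 − 0.07 = 0.47 and 1.44 − 0.07 = 1.37, so about 0.5-1.4 points of 11.

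The per-wart rates in Section 15.1 (26% and 9%) do not belong in this sum, because the endpoint requires all of a subject's warts to be clear.

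**4. Direction and effect on power** (18% against 7%, loss unrelated to outcome, observed rate = p × (1 − loss))

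| Loss active / vehicle | Observed difference | Power |
|---|---|---|
| 0 / 0 | 11.0 points | 96.3% |
| 5% / 0 | 10.1 points | 93.7% |
| 10% / 0 | 9.2 points | 89.7% |
| 10% / 5% | 9.6 points | 92.1% |
| 0 / 10% | 11.7 points | 98.1% |

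Excess loss on active shrinks the observed difference; excess loss on vehicle widens it. For a 10% loss on active only, power runs from 94.6% to 84.0% as the vehicle rate goes from 5% to 9%.

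**The case against.** The strongest reply is that no sentence orders study exit. The termination page is undefined and might record end of treatment; removal in 8.3 is permissive and study withdrawal there is conditional; the Visit 13 limit may only mark how long the prohibition lasts. This stands in part. A reader might infer that the protocol expressly turns a drug stop into a study exit. It does not: it conflates the two. The defect is that sites can follow the text into data loss and nothing in it tells them otherwise.

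Second, most skin reactions are handled without anyone leaving. Section 10.5 holds treatment of a wart with a severe, worsening reaction, and holds an at-home application that is not tolerated. Section 12.3 sends a subject whose wart cannot be assessed to the next scheduled visit. Section 10.8 only records a refused treatment. This stands, and makes permanent withdrawal a residual route.

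Third, a reader might infer that the loss falls mainly on active. The documents do not support that. It is plausible for adverse-event stops, but other wart therapy is more likely where warts persist, which may be more often on vehicle. No rate by arm is given, and Section 5.2 describes Phase 2 events and reactions as mostly mild.

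Fourth, skin-reaction follow-up is not wholly lost: the causal event is monitored, and related events are followed to resolution or a stable outcome (Section 14.2.1). What can be lost is the scheduled grading.

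Fifth, Section 15.1 says dropout is already allowed for. No figure is given, so the loss above cannot be shown to be additional.

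**Conclusion.** The point holds as a conflation of two statuses in 14.2.3, 8.3 and 8.4, with no rule that keeps permanently off-drug subjects in scheduled assessments. Adverse-event stops would plausibly bias efficacy conservatively; use of other wart therapy may work the other way; the net direction is unknown.

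The size is modest: about 0.5-1.4 of 11 points, resting on assumed responder rates of 18% and 7%, assumed stop rates of 3-8% and 1%, and full-rate clearance among stoppers. That last assumption probably makes the figure high for early stops. The trial's power is not seriously threatened at these stop rates. The reasons to act are an interpretable responder result and complete safety data, at little cost. It should be corrected, but it does not invalidate the design.

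**What to change.** Reconcile Sections 14.2.3, 8.3 and 8.4:

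- Record 'stopped study medication', with date and reason, separately from 'withdrew from the study'.
- Complete the termination page only for the latter.
- Ask consenting subjects who are off drug to attend the remaining scheduled visits, at least Visits 10 and 13, for PWA, LSR and the scheduled safety tests.
- For users of prohibited wart therapy, collect the same data and state that clearance after such therapy counts as not Clear in the responder analyses. Section 15.3 sets only missing data to not Clear, so without this rule retaining these subjects would let clearance due to the other therapy count as a response. With it, they keep the result they would have had by leaving before the endpoint visit.

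The rules for when medication is stopped stay as they are. The cost is protocol wording, one CRF field and a few more attended visits from the existing schedule, which some subjects will decline.
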